3.9 Pharmacokinetics

Individual MEDI8897 and palivizumab serum concentrations for each nominal sampling time will be listed and summary descriptive statistics presented by treatment group and cohort (preterm, CHD/CLD) in Season 1, and by treatment group in Season 2, respectively. Geometric mean MEDI8897 serum concentrations will be plotted versus time. Individual MEDI8897 serum concentrations will be graphically illustrated, and summarized, by ADA status.

Further, model-based evaluation of PK, and efficacy extrapolation, will be detailed in a separate PK extrapolation plan and reported outside the CSR.

3.10 Impact on Analyses due to COVID-19 Pandemic

Scheduled visits, subject dosing, blood and nasal sample collection become difficult or impossible to perform according to protocol for subjects remaining in the study during COVID-19 pandemic.

Efforts are ongoing to collect outstanding data via alternative means where possible, when onsite visits cannot be performed. As a result, the following changes have been made to the planned analyses:

- Confirmed or suspected cases of COVID-19 will be listed as AEs and summarized as appropriate.
- An additional sensitivity analysis of medically attended RSV LRTI by Day 151 will be performed by excluding subjects who missed at least 1 active dose or had at least 1 active dose delayed for 7 or more days due to COVID-19 pandemic.
- COVID-19 related protocol deviations will be identifiable in the database with a 'COVID' prefix. COVID-19 related important protocol deviations will be summarized and described separately in the CSR.
- Subjects who miss a visit, miss blood or nasal sample collection, discontinue treatment or withdraw from study due to COVID-19 pandemic will be summarized.

5 AMENDMENT HISTORY

Version	Date	Description of Change	
1.0	26SEP20 19	Initial version	
2.0	05APR20 21	 In section 1, replaced hypotheses testing by objectives to align with protocol v2.0. The study is descriptive by design and there is no formal hypothesis testing, therefore the hypotheses testing was removed to avoid potential confusion. Updated sample size in section 2.2 to align with protocol v2.0. Given the challenge of study enrollment due to the COVID-19 pandemic, the sample size was reduced from originally planned in the protocol. In section 3.1, added primary analysis and Season 2 analysis to allow earlier assessment of Season 1 and Season 2 data; added programming rule for multiple measurements within one scheduled visit to deal with multiple measurements within on scheduled visit for ADA, RSV neutralizing antibody, RSV serology and clinical laboratory data; elaborated the definition of baseline for each season and Season 1 + Season 2; added description about strategy to maintain the blind to ensure trial integrity and the blinding of the Season 2 treatment assignment for CLD/CHD subjects who were randomized to the palivizumab arm in Season 1 In section 3.4.2, added GA groups and updated birth weight categories Added section 3.4.4 Violations and Deviations Added section 3.5 medical History In section 3.5 and 3.6, changed "post dose" to "post 1st dose" for report period of efficacy for clarity. 	

- In section 3.5, removed side-by-side efficacy summaries for Season 1 + Season 2 to align with protocol v2.0. As the incidence of medically attended RSV LRTI and RSV hospitalization (and the relevant HRU) are expected to be lower in Season 2 (infant's second RSV season) than that in Season 1, combining the events from Season 1 and Season 2 may not confer value in addition to the individual summary for each season
- In section 3.5.1, defined a RSV sample analysis window [-7, 14] days for medically attended RSV LRTI based on blinded data review
- In sections 3.5 and section 3.7, clarified the potential bias of directly comparing MEDI8897/MEDI8897 with Palivizumab/Palivizumab: if dropouts in Season 1 are associated with efficacy or safety. If dropouts in Season 1 are associated with efficacy or safety, MEDI8897/MEDI8897 and Palivizumab/Palivizumab are not from the same population.
- Demographics, baseline characteristics, selected efficacy and safety summaries will be provided for CHD subjects and CLD subjects separately.
- Added section 3.5.1.3 Sensitivity Analyses of incidence of medically attended LRTI due to RT-PCR-confirmed RSV to evaluate the impact of wrong treatment, missing and out-ofwindow active doses on the primary efficacy endpoint analysis
- In section 3.5.3, the summary of subjects with at least one medically attended LRTI will be broken down by RSV status only. Clarified rules to define severity among multiple medically attended LRTIs, and among multiple hospitalizations due to any respiratory illness, separately.
- In section 3.6.1, removed HUR summaries for Season 1 + Season 2; removed HRU summaries for the following medically attended LRTI categories: non-RSV LRTI (protocol defined), RSV LRTI (non-protocol defined), non-RSV LRTI (non-protocol defined); added analyses on pre-specified OTC medications (analgesics/antipyretics), prescribed medications

(systemic antibacterial agents), and anti-wheezing medications; removed original analyses on overall prescriptions or OTC medications

- In section 3.6.2, removed caregiver burden summaries for Season 1 + Season 2; removed caregiver burden summaries for the following medically attended LRTI categories: non-RSV LRTI (protocol defined), RSV LRTI (non-protocol defined), non-RSV LRTI (non-protocol defined).
- In section 3.6.3 and section 3.6.4, added box plot for serum antibody levels for all subjects by treatment group and by visit
- In section 3.6.4, added summary of RSV exposure (≥ 4-fold rise in serum antibody levels to any RSV antigen from the previous timepoint); added Post-F antigen for seroresponses in MEDI8897
- In section 3.6.5, updated the scope of genotypic and phenotypic analyses, which will be detailed in a separate virology plan
- In section 3.7, added definition of treatment-emergent AEs for each reporting periodIn section 3.7, clarified the scope of safety summaries for Season 1 + Season 2: Season 1 + Season 2 safety summary would provide 2-year incidence of AE. Considering the potential bias of directly comparing MEDI8897/MEDI8897 with Palivizumab/Palivizumab, only several key safety summaries will be repeated for Season 1 + Season 2.
- In section 3.7.1, updated the definition for non-treatment emergent AE/SAE and clarified that pre-planned surgeries that occur during the study for CHD subjects are a part of nontreatment emergent AE/SAE
- In section 3.7.2, added supplementary analysis of AESI based on SMQs/study-specific PTs, and updated the definition for AESI to align with the Safety Strategy and Management Plan
- In section 3.7.3, changed "skin reactions" to "IP-related skin reactions" and clarified that skin hypersensitivity analyses are included in the IP-related skin reactions

- In section 3.7.5, added "3 days" to time relative to dosing; removed TEAE summaries by vaccine status throughout the study; clarified that Season 1 AEs will also be summarized for CLD subjects, CHD subjects, subjects with GA < 29 weeks, subjects with GA < 29 weeks and without CLD or CHD, and CLD subjects with GA < 32 weeks. The Season 2 AEs will also be provided for CLD subjects, CHD subjects and CLD subjects with GA < 32 weeks. The purpose of adding the new subpopulations is to evaluate safety profile for the infants who are recommended to received palivizumab by American Academy of Pediatrics.
- In section 3.7.6, removed toxicity grade of BUN, since toxicity grade of BUN in not defined in Division of AIDS Table for Grading the Severity of Adult and Pediatric Adverse Events
- In section 3.8, clarified the treatment groups to be included in Season 2 ADA summaries and Season 1 + Season 2 ADA summaries: subjects in MEDI8897/MEDI8897 and Palivizumab/Palivizumab arms only have one baseline ADA measurement, which is the last non-missing measurement prior to 1st dose of Season 1, so corresponding reporting period should be Season 1 + Season 2, instead of Season 2 only. Subjects in Palivizumab/MEDI8897 arm receive MEDI8897 only in Season 2, so their reporting period for ADA to MEDI8897 should be Season 2.
- In section 3.8, clarified that ADA influence of PK will be reported in the CSR (not in a separate PK report); clarified definitions for ADA persistent positive and transient positive.
- In section 3.9, clarified that serum concentrations will be summarized by descriptive statistics within the CSR. Removed reference to non-compartmental method and PK parameters, as PK will be evaluated using a model-based approach only (described in a separate analysis plan and reported outside the CSR). This change has been made prior to DBL for Primary Analysis. Clarified how ADA influence on PK will be evaluated.

Added section 3.10 Impact on Analyses due to COVID-19 Pandemic
• Editorial changes for clarity, including updating "3 months" and "6 months" to "3.0 months" and "6.0 months".
 Added Appendix 2 Analysis Window for ADA/RSV Neutralizing Antibody/RSV Serology
Added Appendix 3 Analysis Window for Clinical Lab Data
 Added Appendix 4 Imputation Rule for Partial Adverse Event Start Date
Added Appendix 5 Imputation Rule for Other Partial Dates

Appendix 1 Elements to Evaluate for Case Definition of Medically Attended RSV LRTI (Protocol defined)

Criteria for meeting the protocol-defined endpoint of Medically Attended RSV LRTI – for subjects without underlying lung disease

Specificity	Sensitivity	Medical Significance
RSV Confirmed:	Documented physical	Objective measures of clinical
Positive by central laboratory	examination findings localizing	severity:
real-time RT-PCR assay	to lower respiratory tract:	Increased respiratory rate
	Rhonchi	Hypoxemia
	• Rales	Acute hypoxic or ventilatory
	Crackles	failure
	Wheeze	New onset apnea
		Nasal flaring
		Retractions
		Grunting
		Dehydration due to respiratory distress

LRTI = lower respiratory tract infection; PE = physical examination; RSV = respiratory syncytial virus; RT-PCR = real time reverse transcriptase-polymerase chain reaction; LRTI = lower respiratory tract infection; Note: One item from each column is required to meet the case definition of RSV LRTI.

Criteria for meeting the protocol-defined endpoint of Medically Attended RSV LRTI – for subjects with underlying Lung Disease (CLD or CHD)

Specificity	Sensitivity	Medical Significance
RSV Confirmed:	Documented physical	Objective measures of clinical
RSV Confirmed: Positive by central laboratory real-time RT-PCR assay	Documented physical examination findings localizing to lower respiratory tract: Rhonchi Rales Crackles Wheeze	severity: Increased respiratory rate Hypoxemia Acute hypoxic or ventilatory failure New onset apnea Nasal flaring Retractions Grunting Dehydration
		Prescription of new or increased (from baseline) dose of medications including bronchodilators, steroids, diuretics, cardiac medications

CHD = congenital heart disease; CLD = chronic lung disease; LRTI = lower respiratory tract infection; RSV = respiratory syncytial virus; RT-PCR = real time reverse transcriptase-polymerase chain reaction; Note: One item from each column is required to meet the case definition of RSV LRTI.

Appendix 2 Analysis Window for ADA/RSV Neutralizing Antibody/RSV Serology

Protocol	Scheduled Study Day	Analysis Windows
Global/Japan	Day 1	≤1
Global/Japan	Day 31	2 - 91
Global/Japan	Day 151	92 - 255
Global/Japan	Day 361	≥ 256
EU	Day 1	≤ 1
EU	Day 151	2 - 255
EU	Day 361	≥ 256

Appendix 3 Analysis Window for Clinical Lab Data

Protocol	Scheduled Study Day	Analysis Windows
Japan	Day 1	≤1
Japan	Day 8	2 - 20
Japan	Day 31	21 - 91
Japan	Day 151	≥ 92

Appendix 4 Imputation Rule for Partial Adverse Event Start Date

If date of last dosing prior to AE onset is known:

- Step 1:
 - Assume (date of last dosing prior to AE + 1 day) if AE started <= 7 days after dosing.
 - Assume (date of last dosing prior to AE + 7 days) if AE started 8 14 days after dosing.
 - Assume (date of last dosing prior to AE + 14 days) if AE started >14 days after dosing.
 - Assume (date of last dosing prior to AE + 1 day) if range of days started after dosing was not selected.
- Step 2: if only year of partial AE start date is known, check if year of partial AE start data is after the imputed AE start date; if year and month of partial AE start date is known, check if year and month of partial AE start data is after the imputed AE start date. If yes, then re-impute the AE start date
 - Assume January 1st if only year of the partial AE start date is known
 - Assume 1st day of the month if year and month of the partial AE start date is known

If date of last dosing prior to AE onset is unknown:

- Partial AE start dates where only the year is known:
 - If year is different from the year of any dose date, assume January 1st;
 - If year is same as the year of a dose date:
 - o Assume (dose date + 1 day) if AE started <= 7 days after dosing.
 - Assume (dose date + 7 days) if AE started 8 14 days after dosing. If the imputed date is after the known AE start year, assume (previous dose date + 13 days).
 - O Assume (dose date + 14 days) if AE started > 14 days after dosing. If the imputed date is after the known AE start year, assume (dose date -1) provided that it is not the first dose date.
 - Assume (dose date + 1 day) if range of days started after dosing was not selected.
- Partial AE start dates where only the month and year are known:
 - If year and month is different from the year and month of any dose date, assume 1st day of the month;
 - If year and month is same as the year and month of a dose date:
 - o Assume (dose date + 1 day) if AE started <= 7 days after dosing.
 - Assume (dose date + 7 days) if AE started 8 14 days after dosing. If the imputed date is after the known AE start month, assume (previous dose date + 13 days).

- O Assume (dose date + 14 days) if AE started >14 days after dosing. If the imputed date is after the known AE start month, assume (dose date -1) provided that it is not the first dose date.
- Assume (dose date + 1 day) if range of days started after dosing was not selected.

Appendix 5 Imputation Rule for Other Partial Dates

- Partial dates where only the year is known: for start dates assume January 1st; for stop dates assume December 31st.
- Partial dates where only the month and year are known: for start dates assume the first of the month; for stop dates assume the end of the month.
- In addition, if a concomitant medication is associated with an AE and with partial dates, the concomitant medication start date will be imputed with the either observed or imputed AE start date. If there are multiple associated AEs, the earliest AE start date will be used for imputation. The concomitant medication end date will be imputed by the rules described above where applies.

SIGNATURE PAGE

This is a representation of an electronic record that was signed electronically and this page is the manifestation of the electronic signature

Document Name: d5290c00005-sap-ed-2			
Document Title:	Statistical Analysis Plan Edition 2		
Document ID:	Doc ID-004076767		
Version Label:	2.0 CURRENT LATEST APPROVED		
Server Date (dd-MMM-yyyy HH:mm 'UTC'Z)	Signed by	Meaning of Signature	
09-Apr-2021 22:27 UTC		Content Approval	
09-Apr-2021 22:23 UTC		Author Approval	

Notes: (1) Document details as stored in ANGEL, an AstraZeneca document management system.

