For various LRTI events, including the primary endpoint, detailed definitions of new onset of events are defined in Table 2. For all medically attended LRTI (RSV, non-RSV, protocoldefined, non-protocol defined), the total number of events for each subject and the percentage of each outcome will be summarized by treatment group on three time-intervals: through 150 days post 1st dose (on the ITT population), after 150 days post 1st dose (on the ITT population with Day 151 visit), through 360 days post 1st dose (on ITT population). In addition, a listing that provides relevant information for subjects with more than one medically attended LRTI event throughout the study will be generated. The listing contains the following information: Age at randomization, Hemisphere, Total number of events, Days post 1st dose, AE verbatim term, Date of AE onset/stop, Days from previous event, Visit setting, Protocol-defined (Y/N), RSV (Y/N), and RSV subtype (when applicable). A similar listing for subjects with more than one medically attended RSV LRTI event (regardless protocol-defined or not) will also be presented.

Table 2 Definition for New Onset of Events

Event	Description	
New onset medically attended RSV LRTI	A new onset medically attended RSV LRTI will be defined as an adverse event (AE) (for which at least one healthcare visit is associated with RSV LRTI) and occurs at least 14 days (and similarly using 30 days) after the resolution date of the previous AE for a medically attended RSV LRTI.	
New onset RSV LRTI hospitalization	A new onset medically attended RSV LRTI hospitalization will be defined as an AE (for which at least one hospitalization is associated with RSV LRTI) and occurs at least 14 days (and similarly using 30 days) after the resolution date of the previous AE for a medically attended RSV LRTI hospitalization.	
New onset medically attended RSV outpatient LRTI	A new onset medically attended RSV outpatient LRTI will be defined as an AE (for which at least one healthcare outpatient visit is associated with RSV LRTI) and occurs at least 14 days (and similarly using 30 days) after the resolution date of the previous AE for a medically attended RSV outpatient LRTI.	
New onset medically attended LRTI	A new onset medically attended LRTI will be defined as an AE of LRTI that occurs after the resolution date of the previous AE for a medically attended LRTI.	

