Duration of each hospitalization will be calculated from the admission or deterioration date to discharge date. If the discharge date is missing because the subject died in the hospital, the duration of that hospital stay will be calculated from admission to the minimum of {Death Date, End-of-Study Date, Data Cutoff Date at the time of Primary Analysis}. Total duration of hospitalization is the cumulated days of each hospital stay throughout the reporting time-period.

Similarly, duration of each ICU admission, use of respiratory support, or use of supplemental oxygen will be calculated from start date to stop date or the end date, and the total duration of each medical intervention for a subject is calculated by summing the duration of all occurrences in the time interval of interest.

In addition to the overall HRU summary, the HRU for medically attended RSV LRTI (Protocol-defined) will be summarized through 150 days post 1st dose, after 150 days post 1st dose, and through 360 days post 1st dose. The same conventions used for the overall summary (eg, patient population included in a specific summary) will be applied for the respective

events and the HRU must occur during the event being summarized. Only the subjects with protocol-defined medically attended RSV LRTI will be included in the summary.

In addition, the number of pre-specified OTC medication (analgesics/antipyretics) use will be summarized by treatment group and overall through one week after dosing. The number of pre-specified prescription medication (systemic antibacterial agents) use; the number of anti-wheezing medication use, and the number of antiviral therapy use will be summarized by treatment group and overall through 150 days post 1st dose. The Anatomical Therapeutic Chemical (ATC) codes for these medications will be provided in a separated file provided by medical monitor prior to DBL for primary analysis.

The number and percentage of subjects with pre-specified prescription medications (systemic antibacterial agents) use through 150 days post dose will be provided. The number of use per subject (for those with the medication use) will be summarized through 150 days post dose using descriptive statistics (mean, median, SD, minimum, and maximum) by treatment group and for all subjects combined.

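### SAP Appendix 5 puts no upper bound on partial stop dates, so exploratory resource-use durations can run too long and separate repeat RSV LRTIs can be merged

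*SAP*

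**What the plan says.** Appendix 5 of the SAP covers partial dates other than AE start dates. For year-only dates it says "Partial dates where only the year is known: for start dates assume January 1st; for stop dates assume December 31st"; where month and year are known, "for start dates assume the first of the month; for stop dates assume the end of the month". Its one refinement concerns medication linked to an AE: "the concomitant medication start date will be imputed with the either observed or imputed AE start date". Nothing in the appendix limits how late an imputed stop date may be.

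Two analyses use those stop dates.

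- **Resource use (SAP Section 3.6.1).** ICU stay, respiratory support and supplemental oxygen are each "calculated from start date to stop date or the end date", then summed per child over the reporting period. For hospital stay there is a bound. Its trigger is "If the discharge date is missing because the subject died in the hospital", and the stay is then "calculated from admission to the minimum of {Death Date, End-of-Study Date, Data Cutoff Date at the time of Primary Analysis", whichever comes first.
- **Repeat RSV LRTI (SAP Section 3.5.3, Table 2; same definition in Section 3.5.1.1).** A later AE counts as a new RSV LRTI only if it "occurs at least 14 days (and similarly using 30 days) after the resolution date of the previous AE for a medically attended RSV LRTI".

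AE start dates are handled separately in Appendix 4, which ties them to dosing, for example: "Assume (date of last dosing prior to AE + 1 day) if AE started <= 7 days after dosing".

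**The concern.** The rule errs in one direction. An imputed stop date is never earlier than the true date and is usually later, so errors accumulate across records instead of cancelling. Read literally, the rule can also give impossible values, such as oxygen continuing after discharge or after death.

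Two outputs are exposed. Resource-use durations become too long, and they are summarized only among children who had the activity, so the denominators are small. The interval between two illnesses becomes too short, because Table 2 measures it from the resolution of the first; a second RSV LRTI can then be absorbed into the first. A start date pulled back to the first of the month can likewise put an in-hospital intervention before the admission.

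**Working it through.** The plan states no figure for the effect of this rule, so there is none to reproduce. Everything below is per affected record.

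**Inputs.** The two Appendix 5 rules, the 14- and 30-day thresholds of Table 2, and the 1.9% RSV hospitalization rate and 300/600 group sizes of SAP Section 2.4. *Assumptions:* true dates are spread evenly over the calendar; the next onset date is fully known; gap = next onset minus resolution date.

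**1. Shift in a stop date.** Shift = imputed date minus true date, over 365 consecutive days (July 2020 to June 2021).

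| What is known | Mean shift | Maximum |
|---|---|---|
| Month and year | 14.7 days | 30 days |
| Year only | 182 days | 364 days |

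**2. One record.** Oxygen from 10 to 14 November is 5 days, counting both ends. A month-only stop date gives 10 to 30 November = 21 days. A month-only start as well gives 1 to 30 November = 30 days. A year-only stop gives 10 November to 31 December = 52 days.

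**3. Effect on a group mean.** At the planned 1.9%, the children hospitalized for RSV would number 0.019 × 300 = 5.7 on palivizumab and 0.019 × 600 = 11.4 on MEDI8897. In a group of six, one month-only stop date moves the mean duration by 14.7/6 ≈ 2.5 days, and one year-only stop date by 182/6 ≈ 30 days. These figures assume no truncation at the end of the reporting period, which the SAP does not spell out.

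**4. Repeat RSV LRTI, day of resolution missing.** In a 30-day month with resolution on day d, the shift is 30 − d.

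- True gap 20 days, 14-day rule: the second event is lost if 20 − (30 − d) < 14, that is d ≤ 23. Probability 23/30 = 77%.
- True gap 40 days, 30-day rule: lost if 40 − (30 − d) < 30, that is d ≤ 19. Probability 19/30 = 63%.

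Over the same 365 calendar days, the share of genuine repeats lost is:

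| True gap (days) | 14-day rule | 30-day rule |
|---|---|---|
| 14 | 97% | not applicable |
| 21 | 74% | not applicable |
| 28 | 51% | not applicable |
| 30 | 44% | 97% |
| 35 | 28% | 80% |
| 42 | 5% | 57% |
| 45 | 0% | 47% |
| 60 | 0% | 0% |

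The loss reaches zero at 14 + 30 = 44 days for the first rule and 30 + 30 = 60 days for the second. With only the year known, a true 60-day gap still fails the 14-day rule in 318/365 = 87% of cases.

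*Example:* resolution 6 November, next onset 4 December. The true gap is 28 days; the imputed gap, from 30 November, is 4 days, so the two illnesses are merged.

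**5. What bounds achieve.** In step 2, if the child died on 18 November, a cap at death gives 9 days instead of 21. If no bounding date falls in that month, the figure stays at 21: a cap removes impossible values but not all of the excess. For Table 2, capping resolution at the day before the next onset would leave a gap of 1 day, which still fails both rules.

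**The case against.** **Bounds exist elsewhere.** Section 3.6.1 caps a hospital stay ended by death. The sentence on ICU, respiratory support and oxygen follows it as a parallel rule, and its end date can fairly be read as the same minimum. For protocol-defined RSV LRTI, resource use must also fall within the event. This stands in part: a reader who infers that the SAP never caps a stop date would be wrong. But the stated trigger is a missing discharge date. A partial date completed under Appendix 5 is no longer missing, and the event's own resolution date may have been imputed by the same rule.

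**Start dates are largely anchored.** AE starts follow Appendix 4, and AE-linked medication takes the AE start. This stands.

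**A reader might infer that analgesic or antipyretic use in the week after dosing would be undercounted**, because a month-only start can be imputed before the dose. The documents do not support that. Section 3.6.1 summarizes use within the week, not use that began in the week. The imputed interval still includes the true start day, so if use means overlap with the window, nobody is lost.

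**Partial dates should be few.** The protocol has telephone contact every two weeks to Day 151, source data verification and data queries. Year-only stop dates should be rare, and the 14-day loss matters only for gaps under 44 days. Repeat events are also listed with dates, so they can be inspected. All this limits the size of the problem; it does not make the rule correct when it is used.

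**Conclusion.** The point holds for stop dates. Appendix 5 has no upper bound, and the Section 3.6.1 minimum is stated for one situation only. Per affected record, the mean excess is about 15 days with the month known and about 182 days with only the year known. A genuine repeat RSV LRTI can be lost with the probabilities shown, depending on the true gap. These figures assume evenly spread dates and no truncation at the period end. The number of partial dates is not given, so the total effect cannot be stated.

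The reach is limited to exploratory resource-use durations and to repeat-event counts and listings. It would be tempting to infer that the main results are at risk. They are not: RSV LRTI and RSV hospitalization incidence count first occurrences, treatment-emergent AE incidence depends on start dates, and no hypothesis is tested. Nor do the documents show that one arm would be favored, since the rule is the same in both. The correction is worth making before database lock because the rule can give impossible values and is cheap to repair.

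**What to change.** 1. In Appendix 5, define an imputed stop date as the earliest of: the rule date, death, end of study, the data cutoff of the analysis being run and, for ICU stay and in-hospital respiratory support or oxygen, discharge. Section 3.6.1 names only the primary analysis cutoff, although three analyses are planned.
2. State that no imputed intervention start may precede the associated admission or AE onset.
3. For Table 2, when a resolution date is partial, report the new-onset count twice: once with the earliest possible resolution date (no earlier than that AE's own onset) and once with the latest. In the example above, if the first AE began before November, 1 November gives a gap of 33 days and two events under both rules; 30 November gives 4 days and one event. State how many events are affected.

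The cost is a few lines in Appendix 5, a note to Table 2, a change to one programming macro and one extra row in the repeat-event table. No new data are needed.
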